### **7.3.2. Clinical Laboratory Evaluations**

Blood and urine samples will be collected for clinical laboratory evaluations (including clinical chemistry, hematology, urinalysis, coagulation, and serology) at the times indicated in the Schedule of Assessments in [Appendix 6](#). Clinical laboratory evaluations are listed in [Appendix 2](#). Additional clinical laboratory evaluations will be performed at other times if judged to be clinically appropriate or if the ongoing review of the data suggests a more detailed assessment of clinical laboratory safety evaluations is required.

Subjects will be asked to provide urine samples for drugs of abuse screen and cotinine test, and will undergo an alcohol breath test at the times indicated in the Schedule of Assessments in [Appendix 6](#). For all female subjects, a pregnancy test will be performed at the times indicated in the Schedule of Assessments in [Appendix 6](#).

An Investigator (or designee) will perform a clinical assessment of all clinical laboratory data.

### 7.3.3. Vital Signs

Supine blood pressure, supine pulse rate, respiratory rate, and oral body temperature will be assessed at the times indicated in the Schedule of Assessments in [Appendix 6](#). Vital signs may also be performed at other times if judged to be clinically appropriate or if the ongoing review of the data suggests a more detailed assessment of vital signs is required.

Day 1 predose blood pressure, pulse rate, and respiratory rate will be measured in triplicate at approximately 2-minute intervals. The median value will be used as the baseline value in the data analysis. All subsequent measurements will be performed singly and repeated once if outside the relevant clinical reference ranges. Oral body temperature will be measured singly.

Subjects must be supine for at least 5 minutes before blood pressure and pulse rate measurements.

### 7.3.4. Electrocardiogram

#### 7.3.4.1. *12-Lead Electrocardiogram*

Resting 12-lead ECGs will be recorded after the subject has been supine and at rest for at least 5 minutes at the times indicated in the Schedule of Assessments in [Appendix 6](#). Single 12-lead ECGs will be repeated 2 more times, and an average taken of the 3 readings, if either of the following criteria apply:

- QTcF value  $> 500$  msec
- QTcF change from the baseline (predose) is  $> 60$  msec.

Additional 12-lead ECGs may be performed at other times if judged to be clinically appropriate or if the ongoing review of the data suggests a more detailed assessment of ECGs is required. The Investigator (or designee) will perform a clinical assessment of each 12-lead ECG.

Day 1 predose 12-lead ECGs will be measured in triplicate at approximately 2-minute intervals. The mean value will be used as the baseline value in the data analysis. All subsequent measurements will be performed singly and repeated 2 more times if outside the relevant clinical reference ranges, as described above.

#### 7.3.4.2. *Continuous 12-lead Electrocardiogram Monitoring*

Continuous 12-lead ECG monitoring (Groups A3 and A4 only) using a digital recorder will take place at the times indicated in the Schedule of Assessments in [Appendix 6](#).

All Continuous ECG data collected on study will be archived without extraction or analysis and will not be reported in the scope of this study.

Subjects will be supine for at least 10 minutes before the extraction timepoint and for 5 minutes from the start of each extraction timepoint (each extraction will last for 5 minutes). Environmental distractions (e.g., television, radio, conversation) should be avoided during the pre-ECG resting period and during ECG recording.

When coinciding, vital signs assessments and PK sampling should always be performed after the ECG extraction time window. If a separate ECG machine is being used for safety assessments described in [Section 7.3.4.1](#), that machine should be in place prior to the extraction window to permit safety ECGs to be recorded irrespective of the extraction window. If the machine is not in place prior to the extraction window, safety ECGs must be recorded after the extraction window. If an integral system is used, safety ECGs may be recorded irrespective of the extraction window.

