## 7. STUDY ASSESSMENTS AND PROCEDURES

Every effort will be made to schedule and perform the procedures as closely as possible to the nominal time, giving considerations to appropriate posture conditions, practical restrictions, and the other procedures to be performed at the same timepoint.

The highest priority procedures will be performed closest to the nominal time. The order of priority for scheduling procedures around a timepoint is (in descending order of priority):

- dosing
- blood samples
- urine samples (for CPT31 assay, males only)
- any other procedures (ECGs will be scheduled before vital signs measurements).

Where activities at a given timepoint coincide, consideration must be given to ensure that the following order of activities is maintained: ECGs, vital signs, blood draws.

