**Appendix 6: Schedule of Assessments**

**Schedule of Assessments**

Study Procedures	Screening Day -28 to Day -2	Day -1	Treatment Period		Follow-up (28-30 days postdose)
			Days 1 to 6		
Informed consent	X				
Inclusion/exclusion criteria	X	X			
Demographic data	X				
Medical and surgical history	X	X a			
Urinary drug screen	X	X			
Alcohol breath test		X			
HIV, hepatitis B, and hepatitis C tests	X				
Serum pregnancy test b	X	X			X
Height and body weight	X c	X			
Study residency:					
Check-in		X			
Check-out			Day 6		
Nonresidential visit	X				X
Study drug administration:					
CPT31 or placebo			Day 1 (0 h)		
Pharmacokinetics:					
Blood sampling d			Day 1 predose, 0.5 h ( $\pm$ 3 min), 1 h ( $\pm$ 6 min), 2 h ( $\pm$ 12 min), 4 h ( $\pm$ 30 min), 6 h ( $\pm$ 30 min), 8 h ( $\pm$ 30 min), 10 h ( $\pm$ 30 min), 12 h ( $\pm$ 30 min), 16 h ( $\pm$ 30 min), Day 2 (24 h, $\pm$ 30 min), Day 3 (48 h, $\pm$ 4 h), Day 4 (72 h, $\pm$ 4 h), Day 5 (96 h, $\pm$ 4 h), and Day 6 (120 h, $\pm$ 4 h)		
Urine sampling d, i			Day 1 predose (spot collection) and 0 to 4 h ( $\pm$ 15 min), 4 to 8 h ( $\pm$ 15 min), Day 1 to Day 2 (8 to 24 h, $\pm$ 15 min), Day 2 to Day 3 (24 to 48 h, $\pm$ 15 min), and Day 3 to Day 4 (48 h to 72 h $\pm$ 15 min)		

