**Schedule of Assessments**

Study Procedures	Screening Day -28 to Day -2	Day -1	Treatment Period		Follow-up (28-30 days postdose)
			Days 1 to 6		
Immunogenicity:					
Blood sampling d			Day 1 predose, Day 2 (24 h), Day 5 (96 h)		X
Safety and tolerability:					
Adverse event recording	X	X	Ongoing		X
Prior/concomitant medication monitoring	X	X	Ongoing		X
Clinical laboratory evaluations (including coagulation) d	X e	X e	Day 2 (24 h), Day 3 (48 h), Day 4 (72 h), Day 5 (96 h), and Day 6 (120 h e )		X
Supine blood pressure, supine pulse rate, respiratory rate and oral body temperature d	X	X	Day 1 predose, 2 h, 4 h, 12 h, Day 2 (24 h), Day 3 (48 h), Day 4 (72 h), Day 5 (96 h), and Day 6 (120 h)		X
12-lead ECG d	X		Day 1 predose, 2 h, 4 h, 12 h, Day 2 (24 h), Day 3 (48 h), Day 4 (72 h), Day 5 (96 h), and Day 6 (120 h)		X
Continuous 12-lead ECG			X f		
Physical examination d	X g		Day 1 predose, Day 2 (24 h), Day 3 (48 h), Day 4 (72 h), Day 5 (96 h), and Day 6 (120 h) h		X h

Abbreviations: ECG = electrocardiogram, h = hour; HIV = human immunodeficiency virus; min = minute.

a Interim medical history.

b In all females.

c Height measured at Screening only.

d Times (h) relative to dosing.

e Clinical laboratory tests to include lipid panel (fasted).

f Monitor for 12-lead ECG recording will be worn from 2 hours predose to 25 hours postdose on Day 1. Extraction timepoints will be 60, 45, and 30 minutes predose and at 0.25 hours, 0.5 hours, 1 hour, 2 hours, 4 hours, 6 hours, 8 hours, 10 hours, 12 hours, 24 hours postdose. Continuous 12-lead ECG will be performed on Groups A3 and A4 only.

g Performed between the Screening Visit and predose assessments.

h Symptom-directed physical examination at all timepoints other than Screening.

iPK urine sampling for males only

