8.5.2. Presentation of Pharmacokinetic Data

8.5.2.1. Presentation of Plasma Drug Concentration Data

If the actual time of sample collection deviates from the nominal time by more than $\pm 10\%$, the concentration will be flagged and excluded from the summary statistics. Individual concentrations deemed to be anomalous will be flagged in the listings and excluded from the summary statistics.

For PK concentration data the following rules will apply:

- Values that are BLQ will be set to 0 for the calculation of summary statistics.
- Arithmetic mean or median values that are BLQ will be presented as 0.
- If any BLQ results (treated as 0) are in a series of summarized data, geometric mean and coefficient of variation (CV%) of geometric mean will be reported as not calculated (NC).

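### In Groups A3 and A4 the 0.5 h ECG extraction, the PK-after-ECG rule and the ± 3 min PK window cannot all be met, so the 0.5 h concentration can drop out of the summaries at 0.12 and 0.24 mg/kg

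*Protocol*

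**What the plan says.** - **Extraction times.** Footnote f of the Schedule of Assessments (Protocol Appendix 6) lists the postdose extractions as "0.25 hours, 0.5 hours, 1 hour, 2 hours, 4 hours, 6 hours, 8 hours, 10 hours, 12 hours, 24 hours postdose". It gives no tolerance. It also says "Continuous 12-lead ECG will be performed on Groups A3 and A4 only".
- **Length and direction.** Protocol Section 7.3.4.2 keeps the subject supine "for 5 minutes from the start of each extraction timepoint (each extraction will last for 5 minutes". The segment therefore runs forward from the nominal time.
- **Order.** The same section says "When coinciding, vital signs assessments and PK sampling should always be performed after the ECG extraction time window".
- **PK window.** The Schedule of Assessments gives the first two postdose PK samples as "0.5 h ( $\pm$ 3 min), 1 h ( $\pm$ 6 min" minutes.
- **General rules.** Protocol Section 7 says "The highest priority procedures will be performed closest to the nominal time" and ranks blood samples above ECGs. It then requires ECGs first, vital signs second and blood draws last when activities coincide.
- **Off-time samples.** SAP Section 8.5.2.1 says "If the actual time of sample collection deviates from the nominal time by more than $\pm 10\%$, the concentration will be flagged and excluded". The exclusion applies to the concentration summaries.
- **Parameters.** SAP Section 8.5.1 bases individual PK parameters on actual elapsed time.
- **Use of the recordings.** Section 7.3.4.2 says the continuous ECG data are archived and are neither extracted nor analyzed in this study. Section 3.4 gives their purpose as supporting a possible thorough QT waiver.

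**The concern.** The 0.5 h draw is the first postdose PK sample. In A3 and A4 it shares its nominal time with an ECG extraction, and the order rule pushes it behind a 5-minute segment although its own window closes after 3 minutes. A site that obeys the order rule breaks the PK window, and the SAP then removes the value from the summaries. A site that keeps the PK time draws blood during the ECG segment, or just before it in the resting period, contrary to the order rule and at some cost to the archived recording.

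The gap would be systematic and tied to dose. The two lower groups have no continuous ECG, and neither the safety 12-lead ECG nor the vital signs are scheduled at 0.5 h, so their 0.5 h sample is free of the conflict. At stake is one planned point of the concentration summaries and mean profiles at 0.12 and 0.24 mg/kg, plus a predictable timing deviation in each affected subject.

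**Working it through.** **Inputs.** Extraction start and PK nominal time: the same hour in Appendix 6. Extraction length: 5 min (Section 7.3.4.2). PK tolerance: 3 min at 0.5 h, 6 min at 1 h, 12 min at 2 h, and 30 min at 4 to 24 h where the two coincide (Appendix 6). SAP limit: 10% of nominal (Section 8.5.2.1). Active subjects: 6 per group (Section 3.1).

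**The plan's own windows.** At 0.5 h: 30 ± 3 = 27 to 33 min. At 1 h: 60 ± 6 = 54 to 66 min. At 2 h: 120 ± 12 = 108 to 132 min. Each tolerance is exactly 10% of nominal (3/30 = 6/60 = 12/120), so at these times the protocol window and the SAP limit agree.

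**Applying the order rule.** Earliest draw = nominal + 5 min. Slack = upper window limit − earliest draw. Deviation = 5 / nominal.

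| Time | Earliest draw (min) | Upper limit (min) | Slack (min) | Deviation | Over 10%? |
|---|---|---|---|---|---|
| 0.5 h | 35 | 33 | −2 | 16.7% | yes |
| 1 h | 65 | 66 | 1 | 8.3% | no |
| 2 h | 125 | 132 | 7 | 4.2% | no |
| 4 h | 245 | 270 | 25 | 2.1% | no |
| 24 h | 1445 | 1470 | 25 | 0.3% | no |

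The 6, 8, 10 and 12 h samples also have 25 min of slack. Of the nine shared postdose times, 0.5 h is the only one with no compliant draw.

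**How early would the extraction have to start?** The documents give no such tolerance, so this is an assumption varied over a range. Earliest draw = start + 5.

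| Start (min) | Earliest draw (min) | In 27 to 33? | Deviation |
|---|---|---|---|
| 30 (as written) | 35 | no | 16.7% |
| 29 | 34 | no | 13.3% |
| 28 | 33 | yes, at the limit | 10.0% |
| 27 | 32 | yes | 6.7% |
| 25 | 30 | yes, at nominal | 0% |

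The conflict disappears only with a start at least 2 minutes early.

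**Subjects affected.** 2 groups × 6 active = 12 of 4 × 6 = 24 active subjects. If all six in a group are drawn at 35 min or later, n = 0 at 0.5 h in that group's summary. SAP Section 8.1.1 withholds everything except n, minimum and maximum when n is below 3, so four late draws out of six already remove the mean.

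**The case against.** The strongest reply is that Section 7 already resolves the matter. Its priority list says which procedure sits nearest nominal time (blood), and its order rule says which comes first (ECG). Read together, the ECG is done slightly early and blood is drawn on time. That is a sensible intention, and a start by 28 min would satisfy both the order rule and the PK window. But no text lets the extraction start before its timepoint. Footnote f fixes it at 0.5 h, and Section 7.3.4.2 counts the 5 minutes forward from there. The reply identifies the right repair but does not show that the plan contains it.

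A second reply is that nothing is extracted in this study, so there is no real window to protect. The archiving statement is there, but the supine periods, extraction times and order rule remain as instructions.

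Third, Section 7.1.1 allows PK times to be changed by agreement with the Sponsor, and continuous ECG starts only at the third group. This makes a deviation in all 12 subjects less certain. It does not remove the contradiction.

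A reader might also infer more than the documents support:

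- **Biased exposure or dose proportionality.** Not supported. Parameters use actual times, the SAP excludes late values only from the concentration summaries, and individual values stay in the listings and profiles. Dose proportionality rests on Cmax and AUC.
- **Loss of a planned comparison of early absorption.** The SAP contains no such analysis. What is lost is a descriptive point.
- **A second impossible sample at 1 h.** A draw at 65 min is inside both the window and the 10% limit. The margin is tight, but the sample is feasible.
- **Harm through the placebo subjects.** Section 7.1.1 says their PK samples are not analyzed, so a late draw there is a deviation with no analytical effect.

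**Conclusion.** The contradiction stands on the text. In A3 and A4 the 0.5 h extraction, its forward 5-minute length, the PK-after-ECG rule and the ± 3 min PK window cannot hold together. The earliest permitted draw is 2 minutes past the limit and 16.7% late.

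If Section 7.3.4.2 is followed, up to 12 active subjects at the two highest planned doses lose their 0.5 h concentration from the summary statistics. They also lose it from the mean profile, on the reading that the mean figures plot those statistics. A1 and A2 keep theirs. The effect on the parameter endpoints is small.

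This rests on two assumptions: the extraction starts at its stated time, and the site gives the order rule precedence over the PK window. It merits correction because the loss is avoidable and falls on only one half of the dose range, but it does not threaten the study's main PK conclusions.

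**What to change.** In footnote f and Section 7.3.4.2, state that where an extraction and a PK sample coincide, the 5-minute extraction ends at or just before the PK nominal time, and that PK sampling keeps its nominal time. For example, use 25 to 30 min for the 0.5 h pair and 55 to 60 min for the 1 h pair. The 25-minute start leaves a 5-minute gap after the 0.25 h segment (15 to 20 min), whereas a 20-minute start would run straight on from it. This wording meets both Section 7 rules and leaves the PK windows and SAP Section 8.5.2.1 unchanged. Widening the 0.5 h PK window alone would not be enough, because a draw at 35 min would still exceed the SAP's 10% limit.

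The cost is a wording change, best made before Group A3 is dosed. No procedure is added, since the recorder is worn from 2 hours predose to 25 hours postdose. The downside is that each ECG segment precedes its paired PK sample by up to about 5 minutes, which any later concentration-QTc analysis of the archive should note.

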### **7.3.5. Physical Examination**

A full physical examination or symptom-directed physical examination will be performed at the timepoints specified in the Schedule of Assessments in [Appendix 6](#).

### **7.3.6. Body Weight**

Body weight (in light clothing) will be recorded at the times indicated in the Schedule of Assessments in [Appendix 6](#).

## **8. SAMPLE SIZE AND DATA ANALYSIS**

### **8.1. Determination of Sample Size**

No formal statistical assessment, in terms of sample size, has been conducted as this is the first time CPT31 is being administered to humans. However, the number of subjects in the present study is common in early clinical pharmacology studies and is considered sufficient to achieve the objectives of the study. A common distribution between active and placebo subjects is 6+2. Buoen et al. (Evaluation of the Cohort Size in Phase I Dose Escalation Trials Based on Laboratory Data, *J Clin Pharmacol* (2003) 43:470-476) investigated the impact of cohort size on Type I error and power in Phase I dose escalation trials based on laboratory data and concluded that “the active cohort size in Phase I dose escalation trials should be between 6 and 10 active subjects.”

### **8.2. Analysis Populations**

#### **8.2.1. Pharmacokinetic Population**

The PK population will include all subjects who received at least 1 dose of CPT31 and have evaluable PK data.

#### **8.2.2. Safety Population**

The Safety population will include all subjects who received at least 1 dose of study treatment (CPT31 or placebo).

### **8.3. Pharmacokinetic Analyses**

Noncompartmental PK analysis will be performed on individual plasma and urine concentration data, using commercial software such as Phoenix® WinNonlin®. Plasma concentrations of CPT31 and PK parameters will be listed and summarized using descriptive

statistics. Urine concentrations of CPT31 will be listed. Individual and mean CPT31 concentration-time profiles will also be presented graphically.

Where data are available, CPT31 dose proportionality will be examined across dose groups. The PK parameters will be analyzed for dose proportionality using a power model approach or analysis of variance (ANOVA) model, as appropriate.

#### 8.4. Safety Analysis

Safety parameters will be listed and summarized using descriptive statistics. The frequency of subjects with QTcB >470 ms or change from baseline >30 ms will be summarized for each treatment. No formal statistical analysis of safety data is planned. Each AE will be coded using the Medical Dictionary for Regulatory Activities.

#### 8.5. Interim Analysis

No formal interim statistical analyses are planned for this study.

## 10. APPENDICES

## Appendix 1: Adverse Event Reporting

### Definitions

An adverse event (AE) is any untoward medical occurrence in a patient or clinical investigation subject administered a pharmaceutical product, which does not necessarily have a causal relationship with this treatment. An AE can therefore be any unfavorable and/or unintended sign (including a clinically significant abnormal laboratory finding), symptom, or disease temporally associated with the use of a study drug, whether or not related to the study drug.

### Assessment of Severity

The Investigator will be asked to provide an assessment of the severity of the AE using the following criteria defined by the Division of AIDS Table for Grading the Severity of Adult and Pediatric Adverse Events, Version 2.1 dated July 2017:

- **Grade 1, Mild:** Usually transient and may require only minimal treatment or therapeutic intervention. The event does not generally interfere with usual activities of daily living.
- **Grade 2, Moderate:** Usually alleviated with additional specific therapeutic intervention. The event interferes with usual activities of daily living, causing discomfort but poses no significant or permanent risk of harm to the subject.
- **Grade 3, Severe:** Interrupts usual activities of daily living, or significantly affects clinical status, or may require intensive therapeutic intervention.
- **Grade 4, Potentially Life-threatening:** The subject was at immediate risk of death from the event as it occurred (i.e., does not include a reaction that might have caused death if it had occurred in a more serious form). For instance, drug-induced hepatitis that resolved without evidence of hepatic failure would not be considered life-threatening even though drug-induced hepatitis can be fatal.
- **Grade 5, Death.**

### Relationship to Study Treatment

The Investigator (or designee) will make a determination of the relationship of the AE to the study drug using a 4-category system according to the following guidelines:

- **Not Related:** The AE is definitely caused by the subject's clinical state or the study procedure/conditions.
- **Unlikely Related:** The temporal association between the AE and the drug is such that the drug is not likely to have any reasonable association with the AE.
- **Possibly Related:** The AE follows a reasonable temporal sequence from the time of drug administration but could have been produced by the subject's clinical state or the study procedures/conditions.

- **Related:** The AE follows a reasonable temporal sequence from administration of the drug, abates upon discontinuation of the drug, follows a known or hypothesized cause-effect relationship, and (if appropriate) reappears when the drug is reintroduced.

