and lower albumin and albumin:globulin ratio) in males administered  $\geq 1$  mg/kg/day and females administered  $\geq 3$  mg/kg/day; and increases in mean IL-1 $\beta$  levels on Day 7 in animals administered 6 mg/kg/day and on Day 28 in males administered  $\geq 1$  mg/kg/day and females administered  $\geq 3$  mg/kg/day. CPT31-related non-adverse microscopic findings were observed in the SC injection sites, kidney, and spleen. Microscopic findings included edema and/or macrophage infiltrates in the SC injection sites (correlating with macroscopic thickening) in animals administered  $\geq 1$  mg/kg/day, slight to moderate focal renal tubular degeneration in males administered  $\geq 3$  mg/kg/day, minimal to slight focal mononuclear cell infiltration in kidney of males administered  $\geq 1$  mg/kg/day, and slightly to moderately increased extramedullary hematopoiesis in spleen of males administered  $\geq 1$  mg/kg/day. All effects exhibited full or partial (SC injection site findings) recovery during the recovery phase. Due to the mild severity of findings and the lack of impact on the health and wellbeing of animals administered up to 6 mg/kg/day, effects for doses up to 6 mg/kg/day were considered non-adverse. Thus, the NOAEL in this study was 6 mg/kg/day. This dose level corresponded to maximum observed plasma concentration ( $C_{max}$ ) and area under the concentration-time curve (AUC) from time zero to 24 hours postdose ( $AUC_{0-24}$ ) values of 6,900 ng/mL (764 nM) and 92,300 hr\*ng/mL (10,223 hr\*nM), respectively, on Day 28 of the dosing phase.

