## **3. INVESTIGATIONAL PLAN**

This will be a single SC dose study.

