### **3.1. Overall Study Design and Plan**

This study will comprise a placebo-controlled, double-blind, single-dose, sequential-group design. Overall, it is planned for 32 healthy subjects to be studied in 4 groups (Groups A1 to A4), with each group consisting of 8 subjects. In each group, 6 subjects will be randomized to receive SC CPT31 and 2 subjects will be randomized to receive matching placebo.

Potential subjects will be screened to assess their eligibility to enter the study within 28 days prior to the first dose administration.

Each subject will participate in 1 treatment period only. Subjects will reside at the Clinical Research Unit (CRU) from Day -1 (the day before dosing) to Day 6. All subjects will return for a Follow-up visit 28 to 30 days after dosing.

Based on the ongoing review of the safety, tolerability, and PK results, additional nonresidential visits may be required. The number of additional visits per subject will not exceed 3 and will not extend beyond 30 days after dose administration.

[figure not shown]
All groups will be divided into 2 cohorts, with each cohort being dosed 72 hours apart. The first (sentinel) cohort will comprise 2 subjects, with 1 subject receiving CPT31 and 1 subject receiving placebo. The second cohort will comprise 6 subjects, with 5 subjects receiving CPT31 and 1 subject receiving placebo.

The maximum total duration of study participation for each subject (from Screening through Follow-up visit) is anticipated to be approximately 8 weeks.

Dose escalation will occur a minimum of 7 days after all subjects complete all Day 6 assessments in the previous dose group.

[figure not shown]
An overview of the study design is shown in [Figure 1](#) and the planned dose levels in are shown in [Figure 2](#). A Schedule of Assessments is presented in [Appendix 6](#).

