### **3.7. Dose Escalation Stopping Rules**

Following discussion among the PSRT, dose escalation will stop if:

- Clinically relevant signs or symptoms of similar nature occur in 2 or more subjects in a group that, in the opinion of the Investigator, warrant stopping of dose escalation.
- One or more subjects experience a serious AE (SAE) that is considered to be related to IMP.
- Two or more subjects experience a Grade 3 or 4 AE or laboratory abnormality that is considered to be at least possibly related to IMP.
- There is evidence of clinically significant increases in liver function tests (aspartate aminotransferase, alanine aminotransferase, alkaline phosphatase, bilirubin, and/or gamma-glutamyl transferase), defined as 3 times the upper limit of normal in 3 or more subjects in a group (confirmed with repeat testing).
- Clinically significant increases in serum creatinine or blood urea nitrogen, defined as 1.5 times and 2 times the upper limit of normal, respectively (confirmed with repeat testing), in 3 or more subjects in a group.

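### *Related* requires abatement on stopping a drug given only once, so a fatal or non-abating event with no alternative cause fits no causality category, and the Section 3.7 SAE criterion is left ambiguous

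*Protocol*

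**What the plan says.** Protocol Appendix 1, Relationship to Study Treatment, asks the investigator to judge each AE "using a 4-category system according to the following guidelines". The definition of *Related* opens "The AE follows a reasonable temporal sequence from administration of the drug, abates upon discontinuation of the drug". From the abatement condition to its end, it reads "abates upon discontinuation of the drug, follows a known or hypothesized cause-effect relationship, and (if appropriate) reappears when the drug is reintroduced". *Possibly Related* needs a plausible time course and an event that "could have been produced by the subject's clinical state or the study procedures/conditions".

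On the design, Section 3 states "This will be a single SC dose study", and Section 3.1 adds "Each subject will participate in 1 treatment period only".

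One of the criteria for stopping escalation in Section 3.7 is "One or more subjects experience a serious AE (SAE) that is considered to be related to IMP". The next criterion, for Grade 3 or 4 events in two or more subjects, extends to events that are at least possibly related.

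SAP Section 8.6.1 defines a treatment-related TEAE by three labels: possibly, probably and definitely. The protocol scale has no *probably* or *definitely*.

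**The concern.** The definition reads as text for repeat dosing. The clause allowing for inapplicability is attached to rechallenge only, so the abatement condition stays mandatory in a study where no treatment is ongoing and none can be stopped.

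Safety is the primary objective of this first-in-human study, and causality is the investigator's main judgement on each event. A category that shuts out events because they end in death or do not improve gets the most serious events wrong. It would matter most if a decision rule depended on that category, and the SAE criterion in Section 3.7 may do so.

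**Working it through.** The documents give no figure to reproduce. The check is a reading of the definitions, with one supporting calculation.

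**1. Structure of *Related*.** There are four elements joined by *and*: timing, abatement on discontinuation, a known or hypothesized mechanism, and rechallenge. Only rechallenge is conditional. With one injection in one treatment period, discontinuation never occurs as an act. Fading after the dose also cannot be told apart from spontaneous resolution.

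**2. A test event run through all four categories.** Take an SAE that starts soon after injection, has a hypothesized mechanism and no alternative cause, and either is fatal or does not lessen.

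- *Not Related* needs a definite cause in the subject's condition or the study procedures: not met.
- *Unlikely Related* needs timing that makes the drug an improbable cause: not met.
- *Possibly Related* needs another explanation that could have produced the event: not met.
- *Related*: timing met, mechanism met, rechallenge waived, abatement not met.

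No category fits. A mechanism can be hypothesized from the protocol itself: in the 14-day rat study (Section 1.4.1), renal tubular degeneration caused death or moribund condition in 16 of the 18 animals that did not survive dosing, one of them in the lowest dose group. Those were repeat doses of at least 10 mg/kg/day, against a highest planned single dose of 0.24 mg/kg, so they show that a mechanism can be named, not that such an event is expected here.

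**3. Can abatement be seen at all after one dose?** Section 3.5 predicts, for dosing every 72 h, a peak of about 50 nM and a trough of 13 to 22 nM. Assuming mono-exponential decline over the interval:

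half-life = 72 × ln 2 / ln(peak/trough)

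- Trough 13 nM: 49.9 / ln(50/13) = 49.9 / 1.347 = 37.0 h; five half-lives = 185 h (7.7 days).
- Trough 22 nM: 49.9 / ln(50/22) = 49.9 / 0.821 = 60.8 h; five half-lives = 304 h (12.7 days).
- Monkey SC half-life of 18.6 h (Section 1.5): five half-lives = 93 h (3.9 days).

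All three fall before the Follow-up visit at 28 to 30 days. An event that fades as the drug clears can therefore be observed, and Section 1.7 says injection site reactions generally resolve within 3 days. Section 1.5 notes that human PK is not yet established, so these are rough values.

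**4. Where causality is used.** These start at *possibly* or an equivalent: study discontinuation for Grade 3/4 events (Section 3.8), unblinding (Section 5.4), AE follow-up, the adverse drug reaction definition and the reporting of later deaths (all Appendix 1), and the SAP's treatment-related summaries. Two places use the bare word *related*: the SAE criterion in Section 3.7 and subject replacement in Section 4.3.

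**5. Section 3.7 for one subject.** Of its five criteria, two need two or more subjects and two need three or more. The SAE criterion is the only one that an event in a single subject can meet. The Grade 3/4 criterion does not name Grade 5.

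**The case against.** The strongest reply is that the definitions are guidelines for judgement, not an algorithm. Exposure ends by itself after one injection, so an investigator may reasonably treat fading during washout as abatement; step 3 shows that this can be observed. To abate also means to lessen, not to vanish. A shrinking nodule has abated, and the 28-day rat finding, "All effects exhibited full or partial (SC injection site findings) recovery during the recovery phase", describes abatement, after daily dosing rather than one dose. All of this stands. Persisting injection-site findings are therefore weak examples unless they show no improvement.

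It is also fair that no planned SAP table separates *Possibly Related* from *Related*, and that Section 3.7 uses ordinary lower-case wording after discussion by the Protocol Safety Review Team (PSRT). Section 3.6 requires clinically significant results to be discussed before escalation, and Section 3.8 allows discontinuation for medical reasons. A fatal SAE would not go unreviewed.

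The reply does not reach the fatal or non-abating event, which fails the condition on any reading of abatement. The safeguards are discretionary, whereas the SAE criterion is meant to be a named trigger. The protocol generally writes *possibly* where it means it, including in the adjacent criterion, so reading *related* there as the scale category is natural, though not certain.

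**Conclusion.** The point holds as a wording defect with a narrow but serious reach. As written, an event that is fatal or does not abate cannot be *Related*, and without an alternative cause it has no fitting category. The number of events affected cannot be estimated from the documents and may be zero among the 24 planned CPT31 subjects. The AE summaries are little affected, because they pool from *possibly* upward, although the SAP's labels do not match the scale and leave out the plain label *Related*.

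The effect on Section 3.7 rests on an assumption: that *related* there means the scale category. If it does, a fatal or persisting SAE could not meet the criterion. If it is used in its ordinary sense, the criterion works, but the text does not say so.

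A reader might infer that no AE at all can be scored *Related*, leaving the top category empty, or that the SAE criterion can never be met. The documents do not support either. The definitions are guidelines, rechallenge is waived where it does not apply, and transient events can be read as abating once exposure ends. The exclusion is confined to events that do not abate.

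**What to change.** Reword *Related* in Appendix 1 to rest on a plausible time course after dosing and a known or hypothesized mechanism. State that lessening as the drug clears supports the category where it can be assessed but is not required. Do not add a condition that study procedures must be excluded as a cause: the injection is itself a procedure, and such a clause would keep injection-site reactions out of the category.

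Then reconcile the relatedness terms: say which scale categories the SAE and Grade 3/4 criteria in Section 3.7 refer to, and replace the SAP's three labels in Section 8.6.1 with those of the 4-category scale. No stopping threshold is proposed here; the passages need to agree with each other.

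The cost is one sentence in Appendix 1, matching terms in Section 3.7 and the SAP, and CRF completion guidance. There are no added procedures or subjects. The downside is that slightly more AEs may be labelled *Related*.
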